#### 10.4.4.1. Adverse Events

##### Definitions

For safety variables, 2 observation periods are defined:

- The pretreatment period is defined as the time from signing the ICF to before the single dose of study drug.
- The treatment period is defined as the time after the single dose of study drug until the end of study (week 16).

Treatment-emergent adverse events are defined as those that are not present at baseline or represent the exacerbation of a pre-existing condition during the treatment period.

##### Analysis

All AEs reported in this study will be coded using the currently available version of the Medical Dictionary for Regulatory Activities (MedDRA®). Coding will be to lowest-level terms. The verbatim text, the preferred term (PT), and the primary system organ class (SOC) will be listed.

Summaries of all TEAEs by treatment group will include:

- The number (n) and percentage (%) of patients with at least 1 TEAE by SOC and PT
- TEAEs by severity (according to the grading scale outlined in Section 9.5.1), presented by SOC and PT
- TEAEs by relationship to treatment (related, not related), presented by SOC and PT

Deaths and other SAEs will be listed and summarized by treatment group.

Treatment-emergent adverse events leading to permanent treatment discontinuation will be listed and summarized by treatment group.

#### 10.4.4.2. Other Safety

##### Vital Signs

Vital signs (temperature, pulse, blood pressure, and respiration rate) will be summarized by baseline and change from baseline to each scheduled assessment time with descriptive statistics.

##### Laboratory Tests

Laboratory test results will be summarized by baseline and change from baseline to each scheduled assessment time with descriptive statistics.

Number and percentage of patients with a potentially clinically significant value (PCSV) at any post-randomization time point will be summarized for each clinical laboratory test.

Shift tables based on baseline normal/abnormal and other tabular and graphical methods may be used to present the results for laboratory tests of interest.

Listings will be provided with flags indicating the out-of-laboratory range values.

#### **10.4.4.3. Treatment Exposure**

This is single-dose study.

#### **10.4.4.4. Treatment Compliance**

As a single-dose trial where patients are dosed in clinic, the patients who are randomized but do not receive study treatment drug will be listed.

#### **10.4.5. Pharmacokinetics**

##### **10.4.5.1. Analysis of Drug Concentration Data**

Descriptive statistics of total REGN1908 and total REGN1909 at each sampling time will be provided. Plots of mean concentrations (linear and log scales) versus time will be presented.

##### **10.4.5.2. Analysis of Pharmacokinetic Parameters**

Descriptive statistics of the calculated PK parameter specified in Section [4.4](#) will be provided.

#### **10.4.6. Analysis of Immunogenicity Data**

Formation of ADA will be assessed in individual patients and per treatment group as follows:

- Possible association between changes in PK profile and the presence of R1908-1909 antibodies will be evaluated to assess the potential impact of anti-R1908-1909 antibodies on drug exposure
- Possible association between AEs and the presence of anti-R1908-1909 antibodies may be evaluated to identify a potential impact of anti-R1908-1909 antibodies on safety. Patients with ADA response categories will be listed and summarized as appropriate

#### **10.4.7. Exposure-Response Analysis**

If appropriate, exploratory analyses investigating the relationship between measures of drug exposure and response (including biomarkers) may be performed.

#### **10.5. Interim Analysis**

No formal interim analysis is planned.[10.4.3.4](#)

## 10.6. Additional Statistical Data Handling Conventions

The following analysis and data conventions will be followed:

Definition of baseline:

The last assessment before the administration of study drug on day 1 will be considered as the baseline evaluation.

General rules for handling missing data:

- Rules for handling missing data for assessment (other than efficacy)
- If the start date of an AE or concomitant medication is incomplete or missing, it will be assumed to have occurred on or after the intake of study medication, except if an incomplete date (eg, month and year) clearly indicates that the event started prior to treatment. If the partial date indicates the same month or year of the intake of study medication date, then the start date by the study medication intake date will be imputed; otherwise, the missing day or month by the first day or the first month will be imputed.
- No imputations for missing laboratory data, ECG data, vital sign data, or physical examination data will be made for the purposes of safety analyses.

Visit windows:

- Assessments taken outside of protocol allowable windows will be displayed according to the case report form (CRF) assessment recorded by the investigator.

Unscheduled assessments:

- Extra assessments (laboratory data or vital signs associated with nonprotocol clinical visits or obtained in the course of investigating or managing AEs) will be included in listings and PCSV tabulations, but not summaries. If more than 1 laboratory value is available for a given visit, the first observation will be used in summaries and all observations will be presented in listings.

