### 4.2. Primary and Secondary Endpoints

The primary endpoint in the study is the time to EAR upon Controlled Cat Allergen Challenge in an EEU on day 8.

The secondary endpoints are:

- Time to EAR upon Controlled Cat Allergen Challenge in an EEU on days 29, 57, and 85
- AUC of the percent change (%/h) in FEV1 induced by a Controlled Cat Allergen Challenge over the exposure interval (%/h) from baseline to the Controlled Cat Allergen Challenge on days 8, 29, 57, and 85
- AUC of the percent change (%/h) in patient-assessed nasal symptoms induced by a Controlled Cat Allergen Challenge over the exposure interval (%/h) from baseline to the Controlled Cat Allergen Challenge on days 8, 29, 57, and 85
- AUC of the percent change (%/h) in patient-assessed ocular symptoms induced by a Controlled Cat Allergen Challenge over the exposure interval (%/h) from baseline to the Controlled Cat Allergen Challenge on days 8, 29, 57, and 85
- Change and percent change in cat allergen quantity as experienced by patients during exposure (measured by  $40 \text{ ng}/\text{m}^3 \times \text{minute ventilation} \times \text{time}$ ) on days 8, 29, 57, and 85
- Incidence rates of treatment-emergent adverse events (TEAEs) and serious TEAEs through end of study

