5.7.1. Adverse Events

The verbatim text, the PT, and the primary SOC will be listed in subject listings. Summaries that include frequencies and proportions of patients reporting AEs will include the PTs and the SOCs.

AEs will also be summarized by relationship to EEU procedure. Also, asthma related AEs, specifically, reported throughout the study will be presented for each treatment group and will be summarized by relationship to EEU procedure. Medications used to treat any asthma related AEs will also be listed and summarized by treatment group.

Period of observation: The observation period will be divided into two segments: pre-treatment and treatment periods. The pre-treatment period is defined as the time between when the subjects

give informed consent to before the single dose of study drug. The on-treatment period is defined as the time after the single dose of study drug until the end of study (week 16).

Day 1 is the first day of investigational product, Day -1 is the day before, and there is no Day 0.

Pre-treatment AEs are defined as AEs that developed or worsened during the pre-treatment period.

Treatment-emergent AEs (TEAEs) are defined as AEs that developed or worsened during the treatment period.

The focus of adverse event reporting in the clinical study report will be on TEAEs.

For details on handling missing data and partial dates, see Section [6](#).

Summaries of all TEAEs in each treatment group will include:

- All TEAEs by system organ class
- Possibly related TEAEs by system organ class
- Possibly related TEAEs by intensity and SOC (recommended)
- Time to first occurrence of any (or selected) TEAE (optional)
- Alert terms: all and possibly related TEAEs (optional)
- Serious adverse events: All and possibly related TEAEs by seriousness criterion
- Serious adverse events: All and possibly related TEAEs by SOC
- Death: All and possibly related TEAEs by SOC
- Other significant adverse events: All and possibly related TEAEs by “other significant” adverse event criterion
- Discontinuation: All and possibly related TEAEs by system organ class
- Non-serious possibly related TEAEs by SOC (mandatory if study includes a German center)

Counts will be provided according to treatment group for each PT within each SOC. Percentages will be calculated using the number of patients from the safety population in each treatment group.

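### The partial-date rule for AE onset ignores the AE end date, so an event that resolved before dosing can be counted as treatment-emergent; SAP Section 6 has no AE date rule to correct this

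*Protocol*

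**What the plan says.** Protocol 10.6 sets the rule for an AE or concomitant medication whose start date is incomplete or missing. It has four parts.

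- Default: "it will be assumed to have occurred on or after the intake of study medication".
- Exception: "except if an incomplete date (eg, month and year) clearly indicates that the event started prior to treatment".
- Dosing-date imputation: the condition is "If the partial date indicates the same month or year of the intake of study medication date". When it is met, the day of dosing becomes the onset date.
- Fallback: "otherwise, the missing day or month by the first day or the first month will be imputed".

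None of the four mentions the end date.

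The SAP section on adverse events (5.7.1) states "For details on handling missing data and partial dates, see Section" (the number given is 6). Within that section, SAP 6.3 covers medication dates and missing TEAE intensity or relationship. It has no rule for AE start dates.

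The output that depends on the rule is a secondary endpoint in Protocol 4.2: "Incidence rates of treatment-emergent adverse events (TEAEs) and serious TEAEs through end of study". The protocol's definition of the term, in 10.4.4.1, is: "Treatment-emergent adverse events are defined as those that are not present at baseline or represent the exacerbation of a pre-existing condition during the treatment period". SAP 5.7.1 defines TEAEs as AEs that began or got worse in the treatment period.

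**The concern.** AEs are recorded from informed consent (Protocol 9.4.1), and screening can begin up to 85 days before dosing. Some AEs will therefore start and end before study drug is given. If such an event has a partial start date that is compatible with the dosing date, the rule places its onset on Day 1 even when a recorded end date shows that it was already over. The result is an impossible record, with onset after resolution. Because treatment-emergent status turns on onset relative to dosing, a screening event then enters the TEAE count.

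The exception does not help here. It considers only the incomplete start date, and a start in the dosing month, or one with only the dosing year known, does not clearly indicate a start before treatment.

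**Working it through.** The plan gives no figure to reproduce, so the check applies the rule to example records and then sizes the exposure.

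**Step 1. Example records, dosing on 20 March.**

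| Start recorded | End recorded | Onset under Protocol 10.6 | Result |
|---|---|---|---|
| March, day unknown | 5 March | 20 March | Onset 20 − 5 = 15 days after the end; counted as TEAE |
| Year only, same year as dosing | 10 February | 20 March | Onset after the end; counted as TEAE |
| February, same year | any | 1 February | Exception applies; pre-treatment |
| December, previous year | any | 1 December | Exception applies; pre-treatment |
| June, same year | any | 1 June or 20 March, depending on reading | TEAE either way |

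The first two rows come out the same however the month-or-year phrase is read. A wholly missing start date is also assumed to fall on or after dosing, so an end date before dosing contradicts it in the same way.

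**Step 2. The ambiguous phrase.** In the hierarchical reading, the month is compared when only the day is missing, and the year is compared when the month is missing too. The June record then falls through to the fallback and gets 1 June. In the literal reading, a matching year is enough, so the record gets 20 March. The gap is 11 (rest of March) + 30 (April) + 31 (May) + 1 = 73 days. The onset is after dosing under both readings, so TEAE status is unchanged.

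**Step 3. How much of screening is exposed.** Assume, since the documents do not say, that dosing is spread evenly over a 365-day year and that pre-dose AE onsets are uniform over the 85 days before dosing.

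- Only the day missing: the average number of pre-dose days in the dosing month is Σ n(n−1)/2 ÷ 365 over months of n days. That is (7×465 + 4×435 + 378)/365 = 5373/365 = 14.7 days. As a share of screening, 14.7/85 = 17%.
- Day and month missing: the average number of pre-dose days in the dosing year is (84×85/2 + 280×85)/365 = 27370/365 = 75.0 days. As a share, 75.0/85 = 88%.

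These are shares of pre-dose onsets that would be moved to Day 1 if their dates were partial in that way. They are upper bounds for the problem, because only events that also ended before dosing yield an impossible record. They say nothing about how many dates are partial.

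**Step 4. Effect on the endpoint.** With 30 patients per arm, one patient wrongly counted adds 1/30 = 3.3 percentage points to that arm's incidence. This holds only if the patient has no genuine TEAE, since the table in Protocol 10.4.4.1 counts patients with at least one.

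**The case against.** The best defence has four parts.

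- **TEAE definition.** Under the SAP definition, an event with a known end before dosing neither began nor worsened on treatment. A careful programmer would exclude it, and data cleaning (Protocol 10.8.1) should query it. This is fair as a prediction of good practice. But status is derived from the imputed onset, neither document states an end-date check, and a query may not recover a date the patient cannot recall.
- **Conservatism.** The rule errs towards counting events and treats both arms alike. This stands: it gives no reason to expect bias in favour of either arm.
- **Rarity.** AEs are collected at every scheduled visit and call, so year-only onsets should be uncommon. Asthmatic and allergic symptoms in response to the EEU are not reported as AEs (Protocol 9.4.1), so the two screening exposures supply fewer candidate events than one might suppose. This also stands.
- **Ordinary reading.** Taken fully literally, the phrase would match the dosing month of a different year, which cannot be intended. The hierarchical reading is the natural one, so the June example is an ambiguity and not a demonstrated error.

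A reader might infer that any AE whose partial date shares the dosing year is moved to Day 1 whatever month is recorded. The documents do not support that: the exception keeps a known earlier month pre-treatment. Nor should the 88% in the working be taken as an error rate, since it is a share of calendar days and applies only when the month is missing.

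**Conclusion.** The point holds for AEs with a recorded end before dosing and a start date known only to the dosing month or the dosing year. For these, the written rule gives an onset later than the end and counts the event as treatment-emergent. Nothing in the SAP corrects it, because the section it cites for partial dates has no AE start-date rule.

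The likely effect is a slight over-count of TEAEs: up to 3.3 points in an arm for each misclassified patient without another TEAE. The number of such records cannot be estimated from the documents and is probably small. The conclusion assumes that treatment-emergent status is programmed from the imputed onset date and that AE end dates are collected.

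The later-month question is separate and lesser. It cannot change TEAE incidence. It matters only for onset timing, such as the time-to-first-TEAE summary that SAP 5.7.1 marks as optional.

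**What to change.** State one AE start-date rule in SAP 6.3, where SAP 5.7.1 already points, and align Protocol 10.6 with it:

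1. Impute the dosing date only if all known parts of the start date match it (same month and year when only the day is missing; same year when the month is also missing) **and** the AE end date is missing or on/after dosing.
2. If the end date is before dosing, classify the AE as pre-treatment.
3. If the known month is after the dosing month, use the first day of that month.

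The cost is a few sentences and one extra condition in the derivation program. No new data or site procedure is needed. The SAP text can be settled on blinded data before database lock, and the protocol wording can follow at the next amendment.

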## 10.7. Statistical Considerations Surrounding the Premature Termination of a Study

If the study is terminated prematurely, only those parameters required for the development program and/or reporting to regulatory authorities will be summarized. Investigator and sponsor responsibilities surrounding the premature termination of a study are presented in Section 15.1.

## 10.8. Data Management and Electronic Systems

### 10.8.1. Data Management

A data management plan specifying all relevant aspects of data processing for the study (including data validation [quality-checking], cleaning, correcting, releasing) will be maintained and stored at Regeneron (Sponsor).

A medical coding plan will specify the processes and the dictionary used for coding. All data coding (eg, AEs, baseline findings, medication, medical history) will be done using internationally recognized and accepted dictionaries.

The CRF data for this study will be collected with Medidata Rave.

#### **10.8.2. Electronic Systems**

Electronic systems that may be used to process and/or collect data in this study will include the following:

- IWRS system – randomization, study drug supply
- Medidata Rave electronic data capture (EDC) System – clinical data capture
- Statistical Analysis System (SAS) – statistical review and analysis
- Pharmacovigilance safety database
- Connected Spirometry

### **11. STUDY MONITORING**

#### **11.1. Monitoring of Study Sites**

The study monitor and/or designee (eg, contract research organization [CRO] monitor) will visit each site prior to enrollment of the first patient, and periodically during the study.

The investigator must allow study-related monitoring.

The study monitors will perform ongoing source data review to verify that data recorded in the CRF by authorized site personnel are accurate, complete, and verifiable from source documents, that the safety and rights of patients are being protected, and that the study is being conducted in accordance with the current, approved protocol version and any other study agreements, ICH GCP, and all applicable regulatory requirements.

#### **11.2. Source Document Requirements**

Investigators are required to prepare and maintain adequate and accurate patient records (source documents).

The investigator must keep all source documents on file with the CRF (throughout this protocol, CRF refers to either a paper CRF or an electronic CRF). Case report forms and source documents must be available at all times for inspection by authorized representatives of the sponsor and regulatory authorities.

#### **11.3. Case Report Form Requirements**

Study data obtained in the course of the clinical study will be recorded on electronic Case Report Forms (eCRFs) within the EDC system by trained site personnel. All required CRFs must be completed for each and every patient enrolled in the study. After review of the clinical data for each patient, the investigator must provide an electronic signature. A copy of each patient CRF

casebook is to be retained by the investigator as part of the study record and must be available at all times for inspection by authorized representatives of the sponsor and regulatory authorities.

Corrections to the CRF will be entered in the CRF by the investigator or an authorized designee. All changes, including date and person performing corrections, will be available via the audit trail, which is part of the EDC system. For corrections made via data queries, a reason for any alteration must be provided.

## **12. AUDITS AND INSPECTIONS**

This study may be subject to a quality assurance audit or inspection by the sponsor or regulatory authorities. Should this occur, the investigator is responsible for:

- Informing the sponsor of a planned inspection by the authorities as soon as notification is received, and authorizing the sponsor's participation in the inspection
- Providing access to all necessary facilities, study data, and documents for the inspection or audit
- Communicating any information arising from inspection by the regulatory authorities to the sponsor immediately
- Taking all appropriate measures requested by the sponsor to resolve the problems found during the audit or inspection
- Documents subject to audit or inspection which include but are not limited to all source documents, CRFs, medical records, correspondence, ICFs, ECs files, documentation of certification and quality control of supporting laboratories, and records relevant to the study maintained in any supporting pharmacy facilities. Conditions of study material storage are also subject to inspection. In addition, representatives of the sponsor may observe the conduct of any aspect of the clinical study or its supporting activities both within and outside of the investigator's institution.
- In all instances, the confidentiality of the data must be respected.

## **13. ETHICAL AND REGULATORY CONSIDERATIONS**

### **13.1. Good Clinical Practice Statement**

It is the responsibility of both the sponsor and the investigator(s) to ensure that this clinical study will be conducted in accordance with the ethical principles that have their origin in the Declaration of Helsinki, and that are consistent with the ICH guidelines for GCP and applicable regulatory requirements.

#### **Informed Consent**

The principles of informed consent are described in ICH guidelines for GCP.

The ICF used by the investigator must be reviewed and approved by the sponsor prior to submission to the appropriate EC. A copy of the EC-approved ICF and documentation of approval must be provided to the sponsor before study drug will be shipped to the study site.

It is the responsibility of the investigator or designee (if acceptable by local regulations) to obtain written informed consent from each patient prior to his/her participation in the study and after the aims, methods, objectives, and potential hazards of the study have been explained to the patient in language that he/she can understand. The ICF should be signed and dated by the patient and by the investigator or authorized designee who reviewed the ICF with the patient.

- Patients who can write but cannot read will have the ICF read to them before signing and dating the ICF.
- Patients who can understand but who can neither write nor read will have the ICF read to them in presence of an impartial witness, who will sign and date the ICF to confirm that informed consent was given.

The original ICF must be retained by the investigator as part of the patient's study record, and a copy of the signed ICF must be given to the patient.

If new safety information results in significant changes in the risk/benefit assessment, the ICF must be reviewed and updated appropriately. All study patients must be informed of the new information and provide their written consent if they wish to continue in the study. The original, signed, revised ICF must be maintained in the patient's study record and a copy must be given to the patient.

